### **6.2.2 Investigation of suspected neonatal late-onset infection**

Detection of LOS in preterm infants is challenging, especially in the absence of laboratory measurement of inflammatory (FBC, CRP) or severe illness (pH, Base excess) markers. The clinical definition of sepsis used here is based on an internally validated score from very preterm (<33 weeks) hospitalised neonates with blood or CSF culture positive sepsis at >72h of age in a similar resource limited setting. The score has sensitivity of 77.1%, PPV 64.9% (AUC0.70, n=497) compared to blood culture and is the considered the most suitable clinical score for the population and local context.

#### **6.2.2.a. Blood cultures**

In the event of a clinical deterioration during hospital admission which meets criteria for possible late onset infection (figure 4), blood cultures will be taken as soon as possible and before antibiotics are started or changed, if possible. If there is a delay in obtaining the biological samples, this will not delay the administration of antibiotics by study site staff. Blood cultures will be taken according to a study specific Biological Samples SSP.

#### **6.2.2.b. CSF cultures**

A lumbar puncture will be performed as soon as possible during normal working hours if late onset infection is suspected according to pre-defined clinical criteria and if there are no clinical contra-indications (raised intracranial pressure; active bleeding; severe cardio-respiratory instability (definitions, page 10); soft tissue infection or congenital malformation at the puncture site). It will be performed in accordance with a study specific Biological Samples SSP.

Both procedures will be carried out with appropriately sized needles and skin antisepsis with precautions to avoid contamination.

### **6.2.3 Environmental surveillance**

Infection control procedures will be regularly documented and environmental surveillance of the neonatal unit and KMC unit will take place at 6 monthly periods at the start of and throughout the study period to identify any external changes in infection control practices affecting outcomes and for future analysis of transmission dynamics. The swab sites will be based on locally available infection control data, possibly include key surface swabs, culture of IV fluids and IV antibiotic vials.

### **6.2.4 Sample labelling, handling & transport**

All biological samples will be collected and handled in a standardised manner according to study specific protocols. Pre-printed labels will be used for each sample and hand labelled with the date and time only. Sample transport logs will be used to document and track the movement of samples between the study site and MRCG Clinical Laboratory.

#### ***Swab samples***

Swab samples will be kept in a temperature monitored fridge at the study site at between +4 and +8°C whilst awaiting transport. Samples will be transported in a temperature monitored transport cool box with ice-packs to the MRC Clinical Laboratory within 6 hours of collection. If samples are taken during out-of-hours periods, they will be stored at the SMAC laboratory at the study site in a temperature monitored fridge at 4 to 8 °C for maximum 48h. The temperature of the transport cool box will be documented at time of leaving the study site and arrival at the MRCG Clinical Laboratory.

Protocol #: 1

---

**Blood culture samples**

Inoculated *BACTEC Peds Plus™/F* culture vials will be transferred to the MRCG Clinical Laboratory as soon as possible. If this is likely to be delayed, the sample will be kept at room temperature and transferred to the lab within 24h

**Cerebro-spinal fluid (CSF) samples**

The CSF samples will be transported to the MRCG Clinical Laboratory within 1h of collection, during normal working hours.

## **7 LABORATORY EVALUATIONS**

### **7.1 Storage of carriage samples for future processing**

Neonatal and maternal/caregiver rectal/recto-vaginal will be vortexed for 30 seconds then divided into two 500 microlitre aliquots with 1 sample including 50 microlitres of glycerol 50% for future microbiological culture. Skin swabs will be stored in original cryovial with no processing.

### **7.2 Evaluation for aetiology of late-onset infection**

#### **7.2.1 Blood culture & antibiotic sensitivity testing**

Blood cultures will be entered into the automated Bactec® 9050 BD machine at MRC Clinical laboratory. All samples showing a positive signal will undergo sub-culture using standard methods and in accordance with MRC Clinical Laboratory SOPs. Antibiotic sensitivity testing will be performed according to CLSI 2017 guidelines. Positive isolation of a recognised neonatal pathogen will be considered to be significant.

#### **7.2.2 Cerebro-spinal fluid (CSF) microscopy & culture**

The CSF sample labelled for microbiological analysis will undergo macroscopy, microscopy, culture and antibiotic sensitivity testing of any isolates, as per MRCG SOP ASSAY-CLA-210. Microscopy will give the cell count and gram stain. Culture will be done with Chocolate, Blood and MacConkey agar media with identification of any isolates according to MRCG SOP ASSAY-CLA-210 and antibiotic sensitivity testing as per MRCG SOP ASSAY-CLA-212.

The CSF sample labelled for biochemistry will be analysed for glucose and protein levels, as standard practice. Any leftover specimen will be stored at -70 °C for future testing to identify bacterial pathogens using molecular techniques (PCR).

Isolation of organisms such as Coagulase Negative Staphylococcus (CONS), Diphteroids, *Bacillus* spp. and mixed growth from blood or CSF culture, will be considered as contaminants but will be identified and documented by laboratory staff.

### **7.3 General considerations**

All laboratory procedures will be carried out according to study specific protocols and in accordance with relevant MRCG Clinical laboratory SOPs. All isolates and samples will be stored at -70 degrees Celsius at the Clinical Laboratory and transferred to biobank in batches for storage at -80 degrees Celsius for future characterisation.

Protocol #: 1

---

## 8 SAFETY CONSIDERATIONS

### 8.1 Monitoring of study participants

All study participants will undergo continuous cardio-respiratory monitoring for minimum 24h after enrolment and until stability criteria are reached using the Nonin 2500A handheld pulse oximeter, which will measure and record oxygen saturation and heart rate. Alarms will be set to detect bradycardia (heart rate <100 bpm), tachycardia (heart rate >200bpm) and hypoxia (SPO2<88%). If at any stage subjects receiving the intervention have features of severe instability (definitions, page 10) which do not improve with tactile stimulation over 5 minutes, they will be removed from skin-to-skin contact and taken to a radiant warmer for further assessment by the study site health workers.. If the subject responds quickly and vital signs normalise and remain within normal range for 15 minutes, the subject can be returned to skin-to-skin position. If the vital signs do not normalise or the subject requires bag-valve-mask ventilation, the baby will remain on the radiant warmer and receive any appropriate interventions and be temporarily withdrawn from intervention arm (section 11.2). The pulse oximeter will remain attached to the subject until he/she meets criteria for being stable (definitions, page 10) and for 24h after an apnoeic event. If a previously stable baby has a clinical deterioration requiring bag-valve-mask ventilation, or meets criteria for severe instability they will re-commence continuous cardio-respiratory monitoring until 24h after the last episode of bag-valve mask ventilation. If a subject is classed as being severely unstable, a research nurse or study site nurse will contact the research clinician or PI (by telephone if at weekend or night) as soon as possible to inform them of the condition for the participant to be screened for possible infection. The management of the baby will be according to the standardised management protocol, as directed by the study site staff.

### 8.2 Adverse events

See definitions, page 10, for general definition of AE. For the purposes of this study, it will include but is not restricted to the following:

- Deterioration in clinical stability, as per study definitions of stability
- Clinical deterioration as per adapted PSBI criteria
- Any other deterioration needing change in management, out-with routine management
- Abnormal investigation
- Detection of congenital malformation not apparent at time of recruitment

AE will be pre-defined and all AE will be recorded in the SMR, Adverse Event Log and eCRF and reported as below.

### 8.3 Serious adverse events (SAEs)

The definition of SAE for this study is:

- Death
- Life threatening event
  - Apnoea needing bag-valve-mask ventilation but not resulting in death
  - Severe instability (as per protocol definition)
  - Any other life threatening situation as assessed by clinician
- At risk of permanent / temporary disability
  - Clinically suspected or microbiologically confirmed meningitis
  - Severe jaundice needing phototherapy/exchange transfusion

Protocol #: 1

---

- Suspected Hypoxic Ischaemic Encephalopathy (moderate-severe)
- Acquired hydrocephalus needing diuretics or surgical intervention
- Re-admission to hospital following discharge and within 28d of age
- Prolonged hospitalisation for 28 days or greater

#### 8.4 Responsibilities for safety

London School of Hygiene & Tropical Medicine is the sponsor for this study. Delegated responsibilities will be assigned locally.

The sponsor (LSHTM) is responsible for the following safety aspects:

- Ensuring that before the study begins there are arrangements in place to allocate responsibilities for the management, monitoring and reporting of the research to be conducted
- Ensuring there are appropriate arrangements in place to record, report and review any significant developments throughout the lifespan of the study
- Management of the adverse event reporting in collaboration with the PI and research team

The principal investigator (PI) will assume responsibility for:

- Reporting all SAEs within agreed timeline to Sponsor and relevant ethics committees
- Provide the sponsor with details of all AEs identified in the protocol as critical to the evaluation of safety within the agreed timeframes specified in the protocol
- Assess each event for causality and seriousness between the research procedures and the adverse event
- Supply the sponsor, relevant ethics committees and other relevant organisations with any supplementary information as requested

The research clinician is responsible for identifying AE, SAEs to the PI within the agreed timeframe and for preparing the SAE reports for submission to the Sponsor. The local safety monitor is responsible for reviewing all SAEs and AEs within the defined time period.

The above responsibilities are based on the LSHTM-SOP-009-01 (SOP. Recording, Managing and reporting Adverse Events for Clinical Trials of Non-Investigational Medicinal Products (Non-CTIMPS)).

#### 8.5 Reporting procedures

To monitor for the incidence of adverse events (AE) during the period of hospitalisation, study personnel will review participants daily.

Any adverse events will be recorded in the standardised medical record and eCRF, including any treatments used by study site staff. Study site staff will be responsible for treating any AE with input from the research clinician and PI, as requested. The research clinician will review all AE and classify serious adverse events according to the protocol. All SAE will be reviewed by the PI or delegate within 24h of notification.

The PI or delegate will send an initial notification to the local safety monitor (LSM), sponsor and Clinical Trials Support Office at MRCG within 24h of first being aware. The initial detailed SAE report will be sent to LSM, sponsor and CTSO within 2 working days if the baby dies, or within 5 working days if the baby does not die. The DSMB will receive a 2 monthly summary safety report of all SAE's, as per DSMB charter. Any SAE thought to be related to the intervention will be reported to the ethics committees within 7 days if it results in death or 14 days if non-fatal. All SAE's resulting in death but not related to

Protocol #: 1

the intervention will be submitted to ethics committees as a monthly summary. All other (non-fatal) SAE's will be reported as an annual safety report to ethics committees and the sponsor.

Reporting procedures will be outlined in an Adverse Event SSP. All SAE reports or other safety reports will be kept as essential documents in the Trial Master File.

## **8.6 Safety oversight**

A local safety monitor and an independent Data Safety Monitoring Board (DSMB) will review all the SAE during the course of the trial, as detailed in section 8.1 & 8.2 and outlined in the DSMB charter.

The local safety monitor will be a consultant paediatrician with experience of neonatal care at the study site and an understanding of the limitations of the current standard care. An independent DSMB will be established consisting of an experienced statistician (chair), a paediatrician or neonatologist and a clinical trialist, all with experience in Sub Saharan Africa. The DSMB will meet in person or remotely before the trial begins, every 6 months during the study, following interim and final analysis and at any other time as requested by DSMB. The DSMB will examine SAEs, rate of enrolment, follow-up and compliance to the intervention. An interim analysis will be suggested to the DSMB, to be conducted when approximately half the intended subjects have been followed-up. As this is an un-blinded study, there will be no code to break. The DSMB will advise the study team on study modification, continuation or termination based on pre-defined stopping rules. The sponsor will receive a yearly update report about the study, including summary of safety issues.

## **9 DISCONTINUATION CRITERIA**

### **9.1 Participant's premature termination of intervention**

#### **9.1.1 Criteria for temporary with-drawal from intervention arm**

Participants will stop the intervention if any of the following criteria apply:

“Stopping criteria”:

1. Severely unstable for >10 minutes if:
  - ✓ SPO2<88% in oxygenAND ≥1 of:
  - ✓ Respiratory rate <20 or > 100 breaths/min
  - ✓ Severe chest in-drawing
  - ✓ Apnoea needing bag-valve-mask ventilation
  - ✓ HR <100 or >200 beats/min

OR CPAP is required on clinical grounds as per Standardised Preterm Management Criteria

2. Any other condition which precludes continuous skin-to-skin contact
  - a. Severe jaundice needing immediate management
  - b. Severe anaemia needing blood transfusion
  - c. Seizures
  - d. Severe abdominal distension
  - e. Omphalitis or infection of the umbilical cord
  - f. Apnoea needing bag-valve-mask ventilation
  - g. Widespread skin infection of baby or caregiver providing skin-to-skin contact
  - h. Mother or caregiver not available or willing to do continuous skin-to-skin contact

Protocol #: 1

---

#### 9.1.2 Criteria for re-starting skin-to-skin contact after temporary withdrawal

It is standard practice at the study site to commence intermittent skin-to-skin contact (KMC) once the baby is stabilising and off oxygen but may still be receiving IV fluids or IV antibiotics. If a baby leaves the intervention arm due to clinical instability but then later improves, they can re-start intermittent skin-to-skin contact once all of the following criteria are met, in-line with the current standard care provided at the study site:

“Re-start” criteria:

- No apnoea requiring bag valve mask ventilation for 24h
- Stable (see definitions, page 10)
- No severe chest in-drawing
- No seizures for 24h
- No abdominal distension
- Not on oxygen
- Not on phototherapy for severe jaundice
- Mother or caregiver available and willing to do skin-to-skin contact
- No health care worker concerns about the clinical condition

If the baby requires IV medications or IV fluids but otherwise meets the re-start criteria, intermittent skin-to-skin contact (KMC) can still be recommended. The baby can be transferred to the KMC unit for continuous skin-to-skin contact once the “re-start” criteria are met (above) and the subject is not receiving IV fluids.

The above criteria for starting intermittent and continuous skin-to-skin contact will apply to the control arm as well as the intervention arm.

#### 9.2 Study discontinuation

Stopping rules will be set by the DSMB prior to the study starting.

### 10 STATISTICAL CONSIDERATIONS

#### 10.1 Sample size

A total of 392 subjects are required to show a 30% relative reduction in the primary outcome of all-cause mortality at 28d (power 80%, alpha=0.05). This is based on feasibility study data indicating a mortality rate in eligible neonates of 56% at 28d of age (adjusted to 48% for an estimated 15% reduction in mortality due to trial processes). The number of subjects lost to follow up is expected to be negligible (<5%), due to the geographical region involved, follow-up system planned and based on feasibility study results. However, the number of subjects lost to follow-up will be reviewed at 3 months of recruitment and any necessary adjustments to the sample size will be made, in collaboration with the DSMB.

With the estimated sample size of 392, all secondary outcomes have a power of at least 70%.

#### 10.2 Recruitment plan & timelines

Based on published admission audit data from the study site and observed prevalence of eligibility criteria in the target population (unpublished data), between 135 - 245 clinically eligible subjects are admitted to the study site annually. It is

## Protocol #: 1

---

expected that mothers and fathers may not be present within 24h of admission in 20% of cases and enhanced sensitization and consenting procedures will be used to overcome this recruitment barrier.

Recruitment will take place over 24 months according to a pre-defined recruitment plan with adjustments for seasonality of preterm/LBW births and local admission rates. The weekly recruitment target will vary from 4 to 6 (average 17 subjects/month). The TSC and DSMB will review the recruitment rate at regular periods and any necessary adjustments to the recruitment plan will be made.

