### *Feasibility study to inform planning of eKMC*

From April to August 2017, a prospective observational feasibility study was conducted at the study site with the aims of understanding the target population and assessing the feasibility of conducting the clinical trial. From this data and previous published audit data from the study site, the clinical trial is considered feasible with an estimated 245 clinically eligible patients admitted per year. Barriers to recruitment are absence of caregiver within 24h of admission (21%), death or severe instability during screening period (23%) and consent refusal (14%). Mortality in eligible subjects at 28d is 56% (14/25) with median age at time of death 3d 2h and 71% (10/14) of all deaths occurred within the first week of admission. The feasibility study also identified key enablers and barriers to the provision of early KMC. These included maternal willingness to practice continuous KMC with good family support and the need for enhanced education of both health care workers and parents about providing early KMC alongside other medical interventions. These results will inform the sensitisation, planning and conduct of the clinical study.

References of literature and data are listed in Section 18.

Protocol #: 1

---

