### **5.4.2 Informed consent**

Informed consent will be sought from the parent/caregivers of all participants for the following neonatal participation: inclusion in the study; collection of socio-demographic data; collection of clinical data; collection of biological samples and randomisation to study arm. Consent will also be taken for the possibility that the parent/caregiver will provide continuous skin-to-skin contact, if randomised to that arm.

The preferred person to provide informed consent for neonatal involvement is the parent. However, it is recognised that this may not be possible within the time-frame due to maternal ill health, admission to another health facility and unavailability of father. An estimated 21% of parents may be unavailable within 24h of neonatal admission (unpublished data). If the parent is not available, it will be explored if there is any alternative caregiver available. This caregiver will most likely be a relative of the mother or father. The caregiver will be given the option of using the study telephone to discuss with the parents. Once the parent is available at the study site, the informed consent process will be repeated with the parent to confirm their consent for their baby to continue participation in the study.

Informed consent for taking maternal/caregiver biological samples will be sought after the neonatal consent procedures have finished and before the intervention begins, using a separate information sheet and consent form.

Impartial and literate witness will be used during consent for illiterate parent/caregivers, as per ICH-GCP guidance.

Further details regarding the informed consent process are detailed in section 11.2.

Protocol #: 1

---

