## **3.3 Sample size**

A total of 392 participants (1:1 ratio) were required to detect a 30% relative reduction in the primary outcome (power 80%, alpha=0.05). This is based on an expected mortality rate of 48%, which was adjusted from observed rates of 56% to account for 15% mortality reduction due to trial implementation. Loss to follow up rates were low (<2%) due to the restricted geographical area, co-ordination of follow-up with routine appointments and re-imbursement of travel expenses.

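### Does the recruitment plan of 17 babies a month undercut the stated sample size of 392 and its 80% power?

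*Protocol*

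**What the plan says.** Protocol 10.1 states the requirement: "A total of 392 subjects are required to show a 30% relative reduction in the primary outcome", with 80% power, alpha 0.05 and control mortality of 48%. SAP 3.3 repeats it: "A total of 392 participants (1:1 ratio) were required to detect a 30% relative reduction".

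Protocol 10.2 gives the supply: "between 135 - 245 clinically eligible subjects are admitted to the study site annually". It sets recruitment over 24 months and gives the pace: "The weekly recruitment target will vary from 4 to 6 (average 17 subjects/month"). It names one barrier and a response to it: "mothers and fathers may not be present within 24h of admission in 20% of cases and enhanced sensitization and consenting procedures will be used". It also commits the steering committee and the DSMB to regular review of the rate, with adjustment of the recruitment plan if needed.

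Protocol 1.1, in the feasibility paragraph, uses one figure: "the clinical trial is considered feasible with an estimated 245 clinically eligible patients admitted per year". It then lists the losses seen: "Barriers to recruitment are absence of caregiver within 24h of admission (21%), death or severe instability during screening period (23%) and consent refusal (14"%).

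Protocol 5.4.2 provides a route around absent parents: "If the parent is not available, it will be explored if there is any alternative caregiver available". Sections 5.7.2 and 5.7.4 let someone other than the mother give skin-to-skin contact.

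**The concern.** The two sections do not visibly join up. Section 10.2 gives a range for the number eligible but a single target, and shows no step between them. Section 1.1 calls the trial feasible on 245 a year, which is the top of that range. The 14% refusal is reported in 1.1 and then disappears from the recruitment plan.

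If the true supply were in the lower or middle part of the range, the trial would close short of 392 in 24 months. A reader who took 80% power from SAP 3.3 might then over-read a non-significant result as evidence against a 30% reduction in mortality. That possibility is why the point deserved a check.

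**Working it through.** **Reproducing 392.** Inputs from Protocol 10.1: p1 = 0.48, p2 = 0.48 × 0.70 = 0.336, difference d = 0.144, mean p = 0.408, power 80%. A two-sided alpha of 0.05 is assumed, since sidedness is not stated.

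- Uncorrected, per arm: n = [1.96√(2 × 0.408 × 0.592) + 0.842√(0.48 × 0.52 + 0.336 × 0.664)]² / 0.144² = 181.7, so 182 per arm and 364 in total.
- Continuity-corrected, per arm: (n/4)[1 + √(1 + 4/(n·d))]² = 195.3, so 196 per arm and **392** in total, an exact match.

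**Target.** 17 × 24 = 408, or 204 a year. The requirement of 392 is 196 a year.

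**Supply over 24 months, by uptake.** Yield = 2 × eligible per year × uptake. The 20% absence is from 10.2 and the 14% refusal from 1.1. The last row treats the two losses as independent.

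| Uptake | 135 a year | 190 a year (midpoint) | 245 a year |
|---|---|---|---|
| Full | 270 | 380 | 490 |
| 14% refusal (× 0.86) | 232 | 327 | 421 |
| 20% absence (× 0.80) | 216 | 304 | 392 |
| Both (× 0.688) | 186 | 261 | 337 |

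**Eligible babies needed per year.** Position in the range = (needed − 135)/110.

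- Full uptake: 196 for 392 (55% of the way up) and 204 for 408 (63%).
- 14% refusal only: 196/0.86 = 228 (84%) and 204/0.86 = 237 (93%).
- Uptake needed at 245 a year: 196/245 = 80% for 392 and 204/245 = 83% for 408.

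**Power at other sizes** (same p1 and p2; corrected, with uncorrected in brackets): 421, 83% (86%); 392, 80% (83%); 380, 79% (82%); 337, 73% (77%); 270, 63% (67%). The protocol's primary test is a chi-squared test with no stated correction. Without a correction, 80% power needs 364 babies. That is 182 eligible a year at full uptake, below the midpoint of 190, or 182/0.86 = 212 with 14% refusal.

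**Weekly target.** 17 × 12/52 = 3.9 a week, a shade under the stated minimum of 4 (4 × 104 = 416 babies). This is a rounding slip.

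**The case for a change.** The strongest case for acting is that the inconsistency lies inside the protocol and does not depend on any loss rate. At 135 or 190 eligible a year, 392 is unreachable in 24 months however well consent goes. Mitigation aimed at absent parents cannot lift 270 or 380 to 392, and it does nothing about refusal. Committee review responds to a shortfall but supplies no expected yield. The SAP fits slow accrual: section 3.4 puts the interim analysis, at 196 babies recruited and followed up, in December 2019, about 19 months after the May 2018 start. Data lock (SAP 3.5) follows the last baby recruited in the study period and is not tied to reaching 392. On this view a short table of yield and power, plus a sentence in SAP 3.3 if the trial closed short, would be cheap and honest.

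Part of this stands. Section 10.2 states no uptake behind 17 a month and omits the refusal rate, and section 1.1 rests on the top figure alone. The interim date is consistent with slow recruitment, though the 196 mark may have been passed earlier and the date does not validate any loss rate.

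The step from there to the stated power does not stand. A shortfall would mean that 392 was missed; it would not make the 392 calculation wrong. The low end of the range is printed in 10.2, so the risk is disclosed, and review of the rate is planned.

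**Conclusion.** No change follows. The protocol states how many babies are needed for 80% power. That number is correct, and it should stay in both documents. Its validity does not depend on accrual.

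The stated range includes values that deliver it: 196 to 204 eligible a year at full uptake, just above the midpoint, and 421 babies in 24 months at 245 a year with 14% refusal. Calling the plan feasible only near the top of the range requires a loss to be imposed first. The yield of 337 at 245 a year further requires that none of the parental absence is overcome, despite the provision for alternative caregivers. Those loss rates carry no denominators in the feasibility paragraph. The documents do not settle whether they overlap, or whether the eligibility range already allows for them; the calculations above assume it does not.

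What remains is missing detail: the uptake that 17 a month assumes (83% at 245 a year) and a mention of the 14% refusal in 10.2. Recruitment ended in April 2020, so writing these down would change no enrolment, estimate, test or conclusion. A sentence in SAP 3.3 would depend on a final number that these documents do not give. If the trial did close short, the 95% confidence intervals required by SAP 4.1 and 6.2 will show the achieved precision directly, and better than a restated design power would.
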